### 2.3 Product Rationale

KDOQI guidelines suggest wrist and distal forearm AVF is the best first option for vascular access, if a patient is expected to need hemodialysis for at least a year. However, the prevalence of forearm AVF is low in the US and the failure of forearm AVFs to mature often results in patients using hemodialysis catheters, AVGs, and upper arm AVF.

The Amplifi System dilates veins by persistently increasing WSS in treated veins and inducing vein wall remodeling through the well understood process of flow-mediated dilation where rapid blood flow results in elevated WSS and nitric oxide (eNOS) release from endothelial cells, leading to vascular smooth muscle cell relaxation. If rapid blood flow is sustained for a period of days to weeks, there is remodeling of the vein wall that is characterized by elastin and collagen fragmentation, endothelial and smooth muscle cell proliferation, and a persistent increase in diameter.

The use of the Amplifi System to dilate veins prior to AVF creation could provide the following benefits for patients:

- **Rapid, robust, and reliable vein dilation** – due to the controlled delivery of high flow, non-pulsatile venous blood to the treated vein, and better control of WSS during the vein maturation period when compared with conventional AVF creation.
- **Improved suitability for AVF creation** – enabling AVF creation in patients who are not suitable to receive an AVF due to small vein diameter, especially in the forearm.
- **Improved AVF maturation** – through AVF creation with larger veins, which has been shown to correlate with improved AVF maturation, and also from high WSS in the AVF inflow artery after connection to a large, low resistance, Amplifi System-treated vein, which could stimulate faster and greater outward remodeling of the AVF inflow artery and result in higher AVF blood flows.
- **Reduced time to AVF maturation and reduced catheter contact time** – by creating AVFs with large veins that mature rapidly and allow for early catheter removal.
- **Prolonged AVF patency** – by creating AVFs with higher blood flows (that are resistant to thrombosis) and larger outflow veins (that are more resistant to

## Clinical Protocol FIH-3

Doc No: CLINP1837  
Revision: D  
DCO No: 25-009  
Effective Date: 02/06/25

stenosis formation).

- **Early identification and treatment or exclusion of vein segments with pre-existing disease** – by identifying vein segments with hypertrophic valves or fibrosis that do not dilate in response to elevated WSS and treating them with angioplasty immediately prior to AVF creation or excluding them from the AVF circuit. This could provide an opportunity to address pre-existing outflow vein problems that would have otherwise gone undetected at the time of AVF creation and could impair AVF maturation.

### 2.4 Proposed Indication for Use

The Amplifi Vein Dilation System is a temporary, ambulatory, extracorporeal blood pump system designed to dilate upper extremity veins in patients with a wrist or forearm cephalic vein diameter of  $\geq 1.7$  and  $\leq 3.2$  mm prior to wrist or forearm arteriovenous fistula creation to improve wrist or forearm arteriovenous fistula maturation.

## 3.0 Prior Bench Testing and First-in-Human Clinical Study

### 3.1 Performance and Safety Testing of Amplifi System

Verification and validation testing for the Amplifi System was conducted to ensure design outputs meet defined design inputs. A high-level summary of Sponsor's testing for the Amplifi System is presented in **Table 1: Performance and Safety Testing**.

**Table 1: Performance and Safety Testing**

Item	Evidence/Meets Standard	Pass/Fail
Design Validation	First-in-human (10 subjects) – Vein diameter increased by over 100%; no serious adverse events	Pass
Biocompatibility	ISO 10993-1:2018 Biological evaluation of medical devices — Part 1: Evaluation and testing within a risk management process	Pass
ETO Sterilization	ISO 11135:2014 and A1:2018 Sterilization of health care products – Ethylene oxide - Requirements for the development, validation, and routine control of a sterilization process for medical devices	Pass
	ISO 10993-7:2008/AMD 1:2019 Biological evaluation of medical devices – Part 7: Ethylene oxide sterilization residuals	Pass
	ISO 11138-1:2017 Sterilization of health care products - Biological indicators - Part 1: General requirements	Pass
Packaging	ASTM D4169 Standard Practice for Performance Testing of Shipping Containers and Systems	Pass
Catheter Design	ISO 10555-1:2013 Intravascular catheters - Sterile and single-	Pass

## Clinical Protocol FIH-3

Doc No: CLINP1837  
Revision: D  
DCO No: 25-009  
Effective Date: 02/06/25

Verification	use intravascular catheters - Part 1: General requirements +AMENDMENT 1 (2017)	
Electrical Safety	IEC/ISO 60601-1:2005 Ed3+C1; C2; A1 Medical Electrical Equipment – Part 1: General Requirements for Basic Safety and Essential Performance	Pass
Software Verification	IEC 62304:2006 Ed.1 +A1 Medical Device Software - Software Life Cycle Processes	Pass
Labeling	ISO 15233-1:2021 Medical devices - Symbols to be used information to be supplied by the manufacturer- Part 1: General requirements	Applied
	ISO 18242:2016 Cardiovascular implants and extracorporeal systems — Centrifugal blood pumps	Applied

### 3.2 First-In-Human Study

A prospective, nonrandomized, single arm First-in-Human (FIH) clinical study was performed at the Sanatorio Italiano Hospital in Asuncion, Paraguay in 2021-2022 under the direction of Principal Investigator [name]. The study sponsor for this research was Artio Medical, Inc., which later transitioned to Amplifi Vascular, Inc. A total of n=10 subjects underwent inpatient treatment with the Amplifi System followed by AVF creation with treated veins. AVF maturation was assessed by duplex ultrasound 2 and 6-weeks after AVF creation.

[figure not shown]
[figure not shown]
Treatment of the first cohort (FIH1; n = 5) was concluded in Q2 2021 with a mean treatment time of 8.6 days. All FIH1 subjects had successful AVF creation with treated veins and 4 out of 5 AVFs matured (based on KDOQI criteria). Treatment of the second cohort (FIH2; n = 5) was concluded in Q3 2022 with a mean treatment time of 6.3 days. All FIH2 subjects had successful AVF creation with treated veins and all AVFs were mature at 2 weeks after AVF creation (based on KDOQI criteria).

#### 3.2.1 Device Performance Outcome

[figure not shown]
[figure not shown]
For both FIH1 and FIH2 the primary performance endpoint was the percent change in the treated cephalic vein diameter from baseline to the end of Amplifi System treatment. As shown in Figure 5, the cephalic vein diameter increased by 105% in FIH1 subjects and 150% in FIH2 subjects during the treatment period. As shown in Figure 6, mean imputed cephalic vein blood flow (as measured in the Proximal Outflow Catheter) increased 186% for FIH1 and 134% for FIH2 during the treatment period.

AVFs were successfully created with treated veins in all FIH1 and FIH2 subjects. As shown in Figure 5, for FIH1 subjects, mean AVF outflow vein diameter increased to 6.3 mm and mean AVF blood flow (imputed from brachial artery blood flow in some FIH1 subjects) increased to 851 mL/min six weeks after AVF creation (Figure 6). As shown in Figure 5 and Figure 6, for FIH2 subjects, mean AVF outflow vein diameter increased to 7.0 mm and mean AVF blood flow (imputed from brachial artery blood flow in all FIH2 subjects) increased to 1,153 mL/min six

weeks after AVF creation. There were no Amplifi System related or procedure-related serious adverse events.

[figure not shown]
**Figure 5: Cephalic Vein Diameter Measurements in FIH1 (left) and FIH2 (right)**

**Figure 6: Blood Flow Measurements in FIH1 (left) and FIH2 (right)**

### 3.2.2 Treatment Duration

In the FIH2, vein diameter experienced rapid dilation, started to level off at 48 hours, and remained constant up to 120 hours of treatment duration as shown in **Figure 7**. Immediate dilation of the vein (as early as less than 24 hours of therapy) is indicative treatment effect in the early stage of vein dilation. With controlled increase of non-pulsatile flow, vein dilation plateaus at around 48-72 hours indicative of vein remodeling with sustained effect up to 120 hours. Based on this data, the proposed treatment duration for Amplifi treatment requires a minimum of 60 hours ( $\pm$  12 hours) of treatment to ensure that optimal vein dilation through remodeling is achieved. The recommended treatment duration of 60 hours ( $\pm$  12 hours) is based on the data that vein dilation remained constant as shown in the plot.

**Figure 7: FIH2 Treatment Duration**

### 3.2.3 Safety Outcome

The primary safety endpoint was freedom from the composite of death, re-hospitalization, bacteremia, Amplifi System-related or AVF-related infection, thromboembolic events, or major bleeding from Amplifi System placement to six weeks after AVF creation. There were no serious adverse events (SAEs), deaths, re-hospitalizations, Amplifi System-related or AVF-related infections, major bleeding, or thromboembolic events from Amplifi System placement to six weeks after AVF creation. **Table 2** outlines all adverse events that occurred in the FIH study. Notably, although none of the events were considered more than mild, a minor pump design modification was incorporated to reduce the need for pump replacement.

## Clinical Protocol FIH-3

Doc No: CLINP1837  
Revision: D  
DCO No: 25-009  
Effective Date: 02/06/25

were out of specification (low) in Pumps that were replaced, likely resulting in reduced washing under the impeller and thrombus formation in the lower bearing gap. Upon completion of the FIH study, an updated assembly process was developed, implemented, tested, and verified. Analysis has confirmed that the lower bearing gap for all Pumps built with the updated manufacturing process have been within specification to date.

The FIH study demonstrated that treatment of upper extremity veins with the Amplifi System prior to AVF creation was feasible and safe, and the treatment resulted in large increases in cephalic vein diameters. AVFs made with treated veins matured quickly and fully. These highly promising results support using the Amplifi System to increase AVF suitability (especially forearm AVF), improve maturation, and reduce time to maturation.

The data on the treatment duration from the FIH2 study was used to design the FIH3 study to further optimize the treatment duration of the Amplifi System and further confirm safe use of the device.

## 4.0 Study Design

This nonrandomized study is designed to confirm the safety and effectiveness of using the Amplifi System for dilating upper extremity veins prior to surgical AVF creation as observed during the FIH study. The working hypothesis for the study is that the cephalic vein in hemodialysis patients can be treated safely with the Amplifi System and the treatment will result in dilation of the cephalic vein, and the treated and dilated cephalic vein can be used to make an AVF and improve AVF maturation.

### 4.1 Study Objectives

The Amplifi System will be assessed and analyzed for effectiveness to demonstrate similar outcome from the earlier First-in-Human Studies with shorter treatment duration. Safety analysis will be performed to confirm that major complications will be in an acceptable range.

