## **14.0 Data Analysis and Statistical Considerations**

### **14.1 Study Size Calculation**

This study is not powered for a specific outcome, given the small number of Subjects in the study. Rather, the goal of this study is to collect additional data on multiple effectiveness and safety measures as described in **Section 4.1 Study Objectives**.

The effectiveness measure of the Study is to determine percent change in cephalic vein diameter from baseline examination (pre-treatment ultrasound) to end treatment (immediately prior to Amplifi System removal and AVF creation, with Amplifi System running at final speed). The Sponsor reviewed results of Amplifi System treatment during the First-in-Human Study and determined that up to ten (10) Inpatient Subjects would be sufficient to evaluate the safety and effectiveness of the Amplifi System.

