#### **14.2.2 Analysis of Effectiveness Measures**

In general, descriptive statistics will be provided. Categorical variables will be summarized using frequencies and percentages of Subjects in each category. Continuous variables will be summarized using descriptive statistics and 95% confidence intervals for means will be computed where appropriate. Statistical modeling will be used to identify potential predictors of treatment success as well as safety events and effectiveness.

A subgroup analysis will be performed for patients who received Amplifi System treatment but have Amplifi System stoppage and AVF creation prior to the specified treatment duration. Patients who received Amplifi treatment at the specified treatment duration (e.g., completed the maximum treatment duration (i.e., 72 hours) without having an AVF created will be reported,

along with the reasons for not having one (e.g., inadequate vein diameter, other factors).

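### The objective promises to demonstrate an outcome similar to the earlier FIH studies, but the protocol never defines similar, and an unpowered, descriptive study of up to ten Subjects cannot support that claim

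*Protocol*

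**What the plan says.** The Objectives row of the synopsis (Section 1.0) and Section 4.1 use the same words: the device is to be assessed for "effectiveness to demonstrate similar outcome from the earlier First-in-Human Studies with shorter treatment duration". Section 4.0 likewise presents the study as confirming what FIH observed.

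Section 14.1 describes a different kind of study. It states: "This study is not powered for a specific outcome, given the small number of Subjects in the study". It adds that "the goal of this study is to collect additional data on multiple effectiveness and safety measures", and cites Section 4.1 as the place where that goal is set out. The same section names one measure ("The effectiveness measure of the Study is to determine percent change in cephalic vein diameter from baseline examination") and reports that the sponsor, having reviewed the FIH results, "determined that up to ten (10) Inpatient Subjects would be sufficient to evaluate the safety and effectiveness of the Amplifi System".

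The synopsis plans general descriptive statistics. Section 14.2.2 plans frequencies and percentages for categorical variables, and for continuous ones says that "95% confidence intervals for means will be computed where appropriate". The protocol gives no allowable difference from FIH, no performance goal and no study-level success rule. The maturation definition in Appendix 1 and the dilation thresholds in Section 4.5 classify individual Subjects only.

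**The concern.** To demonstrate similarity to a historical reference is a confirmatory claim. It needs a stated reference, a largest tolerable difference, and enough precision to exclude anything larger. The protocol supplies none of these, and its sample-size section disclaims the aim. Section 14.1 sends the reader to Section 4.1 for a data-collection goal, but Section 4.1 contains the confirmatory one.

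The stake is the treatment duration. FIH1 and FIH2 had mean treatment times of 8.6 and 6.3 days (Section 3.2), while FIH3 treats for 48 hours, extendable to 60 ± 12 hours (Section 4.3). Whether the shorter course does as well is the main question of FIH3. If the objective stays as worded, the lack of a visible difference in ten Subjects could be reported as demonstrated similarity.

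**Working it through.** **No figure to reproduce.** Section 14.1 gives no alpha, power, SD, margin or formula for its ten Subjects. What can be checked is the precision that ten Subjects provide.

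**Inputs from the protocol**
- FIH maturation: 4/5 in FIH1 and 5/5 in FIH2 (Section 3.2), pooled 9/10.
- FIH diameter change: +105% in FIH1 and +150% in FIH2, five Subjects each (Section 3.2.1). Pooled mean (5 × 105 + 5 × 150)/10 = 127.5%.
- Every FIH Subject gained more than 100%; 7 AVFs were radiocephalic and 3 brachiocephalic; FIH2 baselines were 1.7, 1.9, 1.9, 2.2 and 2.4 mm (Section 3.2.3 Summary).
- FIH3 baseline eligibility: 1.7 to 3.2 mm (Section 4.6).

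**Maturation**
- Exact (Clopper-Pearson) 95% interval for 9/10: 55.5% to 99.7%. For 10/10 the lower limit is 0.025^(1/10) = 69.2%.
- FIH3 9/10 against FIH 9/10, Newcombe interval: the Wilson limits for 9/10 are 59.6% and 98.2%. The lower limit of the difference is −√[(0.900 − 0.596)² + (0.982 − 0.900)²] = −0.315. Identical observed rates therefore remain compatible with a loss of about 31 points.

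**Percent change in diameter.** The SD is not stated, so SDs of 20, 40 and 60 points are assumed, common to both studies.

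| 95% half-width (points) | SD 20 | SD 40 | SD 60 |
|---|---|---|---|
| FIH3 mean alone, n = 10: t(9) × SD/√10 | 14 | 29 | 43 |
| FIH3 vs all ten FIH: 2.101 × SD × √(1/10 + 1/10) | 19 | 38 | 56 |
| FIH3 vs FIH2 only: 2.160 × SD × √(1/10 + 1/5) | 24 | 47 | 71 |

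The FIH figures partly bound the SD.
- In FIH1, a mean of 105% with every value above 100% limits the SD to about 11 points (extreme case: four Subjects at 100%, one at 125%).
- FIH2 is barely bounded (four at 100%, one at 350% gives 112 points).
- The ten pooled have an SD between 23.7 (no spread within cohorts) and 78.6 (both extremes together). The half-width against all ten FIH Subjects is then 22 to 74 points, or about 17% to 58% of the 127.5% mean gain.

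So ten Subjects might or might not exclude a material loss of dilation. The protocol does not give the information needed to tell.

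**Comparability of percent change.** The mean FIH2 baseline is 10.1/5 = 2.02 mm. As an illustration, +150% of that is 3.03 mm. The same 3.03 mm gain from 3.2 mm, the top of the FIH3 range, is 3.03/3.2 = about +95%. A fall in percent change could therefore reflect wider baseline veins and not the shorter treatment.

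**The case against.** The strongest defence is that the limitation is disclosed. Section 14.1 openly says the study is unpowered and collects data, it names Section 4.1 as the source of that goal, and every planned analysis is descriptive. On that reading only one verb is too strong. Part of this stands: there is no miscalculated sample size and no hidden test. But the cross-reference does not resolve the conflict, because the section it points to states the confirmatory aim, and the synopsis repeats it.

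The second defence is that a side-by-side with FIH and the form of the intervals may sit in the SAP, which is not shown. That also stands, so their absence from Section 14.2.2 is not a defect in itself. A SAP cannot, however, reconcile two sections of the protocol.

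Several stronger readings are tempting but not supported:
- *Ten Subjects cannot exclude a large loss on any measure.* This is shown for maturation only. For diameter change it depends on the unstated SD.
- *Almost any result could be called similar.* FIH1 and FIH2 do differ by 45 points, but all ten FIH Subjects exceeded 100%, so a mean gain of 30% or 50% would plainly fall outside that experience.
- *A test would miss a real drop.* With true FIH3 maturation of 60%, a Fisher test against 9/10 would be non-significant 94.5% of the time (83% at a true 50%). The arithmetic is right, but the protocol proposes no such test.
- *The working hypothesis in Section 4.0 is a further similarity claim.* It concerns improving maturation and says nothing about similarity to FIH.

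**Conclusion.** The point holds as a conflict between the stated objective and the design. The protocol promises a demonstration of similarity, leaves the term undefined, and elsewhere says the study is unpowered and descriptive. It should be corrected, but it does not invalidate the data to be collected, and ten Subjects is a legitimate size for estimation.

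The maturation result needs no assumed SD, but its 9/10 reference is imperfect: it includes three brachiocephalic AVFs, whereas FIH3 measures forearm AVF maturation, and Section 3.2 ties the FIH2 result to 2 weeks but gives no time for the 4/5 in FIH1. The diameter half-widths rest on an assumed common SD and approximately normal data. That no comparison with FIH is planned is established for the protocol only.

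**What to change.** 1. In Sections 1.0 and 4.1, replace *to demonstrate similar outcome from* with: to estimate vein dilation and AVF maturation with shorter treatment and describe them alongside (the earlier FIH studies).
2. In Section 14.2.2, specify exact 95% confidence intervals for the maturation percentages, and 95% confidence intervals for mean diameter change in both mm and percent. Show them beside FIH1 and FIH2 separately, with baseline diameters and AVF location.
3. In the same section, state that similarity will not be concluded from overlapping results or from a non-significant difference.
4. Do not make an unadjusted FIH3-minus-FIH difference in percent change the test of similarity, because FIH3 admits wider baseline veins than FIH2 had.

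The cost is wording in three places and a few intervals from data already planned, with no additional Subjects. The downside is a more modest effectiveness claim.

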## 1.0 Protocol Synopsis

INVESTIGATIONAL DEVICE	Amplifi™ Vein Dilation System (“Amplifi System”)
STUDY TITLE	Effect of Amplifi™ Vein Dilation System Treatment on Radiocephalic AVF Maturation- (FIH3)
STUDY DESCRIPTION	
Prospective, nonrandomized, single-arm, open-label clinical study (the “Study”) in patients with end-stage renal disease (ESRD) receiving maintenance hemodialysis using a catheter for vascular access (“Subjects”). Patients who are indicated for creation of a forearm radiocephalic AVF based on an Investigator’s standard practice and who have a forearm cephalic vein diameter of <math>\geq 1.7</math> mm and <math>\leq 3.2</math> mm at the proposed Study AVF creation site will be enrolled in the study.
 
The Subjects will be treated in an inpatient (hospital) setting and will receive Amplifi System treatment and undergo subsequent AVF creation (a “Study AVF”) immediately after treatment. Amplifi System removal immediately followed by AVF creation will be performed when Subject had:
 

• Amplifi treatment for <math>\geq 48</math> hours duration and that cephalic vein is suitable for AVF creation determined by physician (e.g., vein diameter <math>\geq 3.3</math> mm as defined in Dageforde as Quartile 3 and baseline diameter increased <math>\geq 50\%</math>); or

• Amplifi treatment could be extended up to 60 hours (<math>\pm 12</math>hrs) if the cephalic vein was not determined to be adequate by the investigator.

 
Data will be collected at screening, baseline, during Amplifi System implantation, during Amplifi System treatment, during Amplifi System removal and AVF creation, and follow-up patient visits at 1, 2 and 6 weeks after AVF creation.

OBJECTIVES	The Amplifi System will be assessed and analyzed for effectiveness to demonstrate similar outcome from the earlier First-in-Human Studies with shorter treatment duration. Safety analysis will be performed to confirm that major adverse events will be in an acceptable range.
INDICATIONS FOR USE	The Amplifi Vein Dilation System is a temporary, ambulatory, extracorporeal blood pump system designed to dilate upper extremity veins in patients with a forearm cephalic vein diameter of $\geq 1.7$ mm and $\leq 3.2$ mm prior to forearm arteriovenous fistula creation to increase vein diameter and improve forearm arteriovenous fistula maturation.

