**Clinical Protocol**  
**FIH-3**

Doc No: CLINP1837  
Revision: D  
DCO No: 25-009  
Effective Date: 02/06/25

	
Rate of Occurrence of Cannulation-related Complications [Timeframe: from AVF creation through end of follow-up period]

EXPLORATORY TECHNICAL PERFORMANCE MEASURES	
Rate of Occurrence of Amplifi System Treatment Failure [Timeframe: from device implantation through less than required minimum treatment hours of duration (e.g., 48 hours)]
 
Rate of Occurrence of Amplifi System component replacement [Timeframe: from device implantation through device removal and AVF creation]
 
Rate of Occurrence of Pump Stoppages and Device Malfunction [Timeframe: from device implantation through device removal and AVF creation]

NUMBER OF SUBJECTS	Up to n=10 Subjects, all Treatment Subjects
STUDY DURATION	All Subjects will be followed for 1, 2 and 6-weeks post AVF creation or to a censoring event (including return of kidney function, kidney transplant, death, loss to follow-up, or Study end) whichever occurs first.
INCLUSION CRITERIA	

1. Age <math>\geq</math> 18 years

2. Indicated for wrist or distal forearm radiocephalic AVF creation based on Investigator's standard practice

3. ESRD currently receiving maintenance hemodialysis via a tunneled, cuffed hemodialysis catheter

4. Baseline wrist or distal forearm cephalic vein diameter of <math>\geq</math> 1.7 mm and <math>\leq</math> 3.2 mm at the proposed Study AVF creation site, wherein the wrist or forearm cephalic vein at the proposed Study AVF creation site is suitable for Amplifi Distal Outflow Catheter placement and Amplifi System treatment, including:

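### The safety objective promises to confirm an acceptable major-event range, but no range is stated, and with up to ten Subjects even zero events could not support a ceiling below about 26–31%

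*Protocol*

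**What the plan says.** The safety objective appears twice. Section 4.1 has "Safety analysis will be performed to confirm that major complications will be in an acceptable range", and the synopsis (1.0) has "Safety analysis will be performed to confirm that major adverse events will be in an acceptable range". Section 4.0 opens in the same vein: "This nonrandomized study is designed to confirm the safety and effectiveness of using the Amplifi System", with reference to what the earlier first-in-human (FIH) study showed.

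The matching measure in 4.5 is the rate of Major Device-Related Adverse Events, a composite counted from implantation to 30 days after device removal and AVF creation. Appendix 1 defines the components. Neither place gives a rate that would count as acceptable.

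The synopsis sets the size: "Up to n=10 Subjects, all Treatment Subjects". Section 14.1 says "This study is not powered for a specific outcome, given the small number of Subjects in the study" and describes the goal as collecting further data, pointing back to 4.1. It then reports that the sponsor reviewed the earlier results and "determined that up to ten (10) Inpatient Subjects would be sufficient to evaluate the safety and effectiveness of the Amplifi System". Section 14.2.3 plans descriptive summaries, with counts and percentages of Subjects by event type. The only interval named in the statistical section is in 14.2.2: "95% confidence intervals for means will be computed where appropriate".

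**The concern.** To confirm that a rate lies in an acceptable range, a study needs a stated range and enough information to exclude rates outside it. This protocol provides no range, and its own section 14.1 disclaims power for a specific outcome. The objective and the statistical section therefore describe two different studies, one that confirms and one that describes.

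What is at stake is what the trial may conclude. With no limit fixed in advance, the objective gives no result that would count as failing it. It also leaves a study with few or no events open to being read as having met a safety criterion that never existed.

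**Working it through.** **The plan's own figure.** The only figure is up to ten Subjects (1.0, 4.3, 14.1). No event rate, margin, confidence level or power lies behind it, so it can be neither reproduced nor refuted by a sample-size formula. What can be calculated is the precision that ten Subjects give.

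**Inputs and assumptions.** n = 10, single arm, one yes/no outcome per Subject (any Major Device-Related Adverse Event), all ten evaluable. The protocol names a 95% level only for means, so applying 95% to the event rate is an assumption. Both two-sided and one-sided limits are shown.

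**Step 1: no events in ten.** The exact (Clopper-Pearson) upper limit is 1 − a^(1/n).
- Two-sided 95%: 1 − 0.025^(1/10) = 0.3085, i.e. 30.8%.
- One-sided 95%: 1 − 0.05^(1/10) = 0.2589, i.e. 25.9%.

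**Step 2: one event in ten.**
- Lower limit: 1 − 0.975^(1/10) = 0.0025, i.e. 0.3%.
- Upper limit: the p solving (1 − p)^10 + 10p(1 − p)^9 = 0.025, which is 0.445, i.e. 44.5%.

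**Step 3: how often a clean result arises by chance.** P(no events) = (1 − p)^10.
- True rate 10%: 0.9^10 = 0.349.
- True rate 15%: 0.85^10 = 0.197.
- True rate 20%: 0.8^10 = 0.107.

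**Step 4: fewer than ten.** The size is a maximum. No events in eight gives a two-sided upper limit of 1 − 0.025^(1/8) = 36.9%; no events in five gives 1 − 0.025^(1/5) = 52.2%.

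**Step 5: Subjects needed, with no events, to bring the upper limit to an assumed ceiling.** n = ln(a)/ln(1 − ceiling), rounded up. The ceilings are illustrative, because the protocol gives none.

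| Assumed ceiling | Two-sided 95% | One-sided 95% |
|---|---|---|
| 30% | 11 | 9 |
| 20% | 17 | 14 |
| 10% | 36 | 29 |
| 5% | 72 | 59 |

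With ten Subjects and no events, the lowest ceiling that can be supported is about 31% (two-sided) or 26% (one-sided).

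**The case against.** The strongest reply is that the protocol already disclaims what is criticised. Section 14.1 says the study is not powered, the synopsis plans descriptive statistics, and there is no test or success rule. In 4.0 the verb confirm is tied to the earlier FIH findings, so it can be read as replication rather than as exclusion of a rate. An Independent Safety Board also watches conduct and may advise on continuation. All of this is true, and it shows that the analysis is modest. It does not supply the missing range: the board is given no limit in this document, and 1.0 and 4.1 still promise a finding that the analysis does not aim at. Nor is this a detail for an unseen SAP, because a range named in an objective belongs with that objective.

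Several stronger readings are tempting but not supported:
- **That ten Subjects is too few, or that 14.1 claims ten can confirm safety.** Section 14.1 ties sufficiency to evaluating, not confirming, and ten can be reasonable for an early study.
- **That the rates in Appendix 2 are the intended range, or make any verdict possible.** They are mostly single event types for other catheters and pumps, not rates for this composite, and the protocol sets no limit from them.
- **That the maturation claim fails in the same way.** Section 4.0 offers "the treated and dilated cephalic vein can be used to make an AVF and improve AVF maturation" only as part of a working hypothesis, and 4.1 names the earlier FIH results as the effectiveness reference. The maturation figures by vein-size quartile in 2.1 are Kaplan-Meier estimates for upper-arm fistulas, not the forearm ultrasound endpoint.
- **That the protocol must prescribe intervals for every proportion.** That can be left to the SAP.
- **That a clean result will be reported as proven safety.** The document leaves room for this but does not fix it.

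Pooling with the ten earlier subjects would help only in part. If all twenty were event-free on one definition, the two-sided upper limit would be 1 − 0.025^(1/20) = 16.8%. The earlier safety composite and the treatment duration both differ, so this is an assumption that the protocol does not make.

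**Conclusion.** The point holds for the safety objective. As written, 1.0 and 4.1 promise confirmation against a standard that is not stated, and they contradict 14.1 and 14.2.3. Stating a range would not by itself rescue the verb: at the 95% level, even the best possible outcome in ten Subjects leaves rates up to 30.8% (two-sided) or 25.9% (one-sided) unexcluded, and one event raises the two-sided limit to 44.5%.

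These figures rest on a 95% level, a per-Subject yes/no outcome and ten evaluable Subjects; fewer Subjects make them worse. The conclusion concerns what the trial may claim. It is not a finding that the device is unsafe or that enrolment should grow.

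**What to change.** - **1.0 and 4.1:** replace the promise to confirm an acceptable range with an objective to estimate the Major Device-Related Adverse Event rate with an exact two-sided 95% confidence interval. Naming the measure also ties together the two terms now used, major adverse events and major complications.
- **4.0:** bring the verb confirm into line with that estimation aim.
- **14.1:** replace the unsupported statement that ten Subjects are sufficient with the precision delivered: no events in ten gives an upper limit of 30.8%; one event gives 44.5%; the limits are wider if fewer than ten enrol.

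This needs no added Subjects, visits or procedures, only a protocol wording change and one standard interval. The downside is that the stated safety claim becomes more modest.
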